4.6. Accountability of the investigational product

The investigator is responsible for complying with the routine rules for handling drug products in the healthcare institution.

4.7. Storage and disclosure of randomization / screening numbers

Not applicable.

4.8. The list of all data that are recorded directly in the CRF and considered primary

In this study, all data will be recorded in the primary documentation before entry into the CRF.

All information that is recorded in the CRF is first entered into the patient's primary medical documentation — the patient's medical record, laboratory analysis forms, etc. An electronic data collection system can also be used to collect primary data (for example, the results of filling in specialized scales).

5. SCREENING AND WITHDRAWAL OF THE SUBJECTS

5.1. Inclusion criteria

1. The patient is already receiving, or the patient have been prescribed therapy with Polyoxidonium® in accordance with the approved labelling in combination with COVID-19 therapy recommended by the Ministry of Health of the Russian Federation.
2. Verified diagnosis: COVID-19.
3. Severity of the disease at hospitalization:
 - severe disease: requiring mechanical ventilation or oxygen, a $SpO_2 \leq 94\%$ on room air or tachypnoea (respiratory rate ≥ 24 breaths/min).
 - mild-moderate disease: $SpO_2 \geq 94\%$ and respiratory rate ≤ 24 breaths/min without supplemental oxygen.
4. Patients who signed the informed consent.
5. Understands and agrees to comply with planned study procedures.
6. Age ≥ 18 years old at the enrolment.
7. Has laboratory-confirmed SARS-CoV-2 infection as determined by PCR, or other commercial or public health assay in any specimen prior to the enrolment.

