ENROLLMENT CRITERIA	
INCLUSION CRITERIA
 
 1. The patient is taking or have been prescribed Polyoxidonium® in accordance with the approved labelling in combination with COVID-19 therapy recommended by the Ministry of Health of the Russian Federation. 2. Verified diagnosis: COVID-19 . 3. Severity of the disease at hospitalization: 
 – severe disease: requiring mechanical ventilation or oxygen, a SpO₂ ≤ 94% on room air or tachypnoea (respiratory rate ≥ 24 breaths/min) – mild-moderate disease: SpO₂ ≥ 94% and respiratory rate ≤ 24 breaths/min without supplemental oxygen. 4. Patients who signed the informed consent. 5. Understands and agrees to comply with planned study procedures. 6. Age ≥18 years old at the enrolment. 7. Has laboratory-confirmed SARS-CoV-2 infection as determined by PCR, or other commercial or public health assay in any specimen prior to enrolment. 
EXCLUSION CRITERIA
 
 1. Pregnancy and lactation. 2. Pathological conditions that make participation in the study impossible for the patient (as judged by the investigator). 3. Participation in any other clinical study during this study, including participation in a clinical study within 30 days before the informed consent. 4. Increased sensitivity to any component of the investigational product. 5. Acute or chronic renal failure. 
WITHDRAWAL CRITERIA
 
 1. The investigator decided that withdrawal from the study is in the patient's interests. 2. Withdrawal of the informed consent (the patient does not want to continue participation in the study). 3. Serious deviation from the study protocol. 4. Idiosyncrasy to the investigational products that developed during the treatment period. 5. AE/SAE that requires an examination and/or treatment that would affect the study procedures significantly. 6. Patient non-compliance. 7. The patient was enrolled by mistake. 8. The patient receives/needs an additional treatment that could affects result of the study or the patient safety. 9. Other conditions or events that require patient withdrawal, as judged by the study doctor.
INVESTIGATIONA	INVESTIGATIONAL PRODUCT

L

**PRODUCT,
DOSAGE,
TREATMENT
REGIMEN**

Polyoxidonium® (azoximer bromide), lyophilizate for solution for injections and topical application.

DOSAGE

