6.2. Description of the visits

A comprehensive description of visits (by days) is provided in Appendix 1. All procedures described below should be carried out as part of the routine practice of the health care institution.

Preliminary evaluation of the inclusion/exclusion criteria

(Before the study initiation)

Full list of the procedures is provided in Appendix 1.

- Signing of informed consent.
- Confirmation of the positive test for SARS-CoV-2¹.
- Collection of patient history, demographics, and anthropometric data.
- Collection of information about previous/concomitant treatments.
- Physical examination (including lung auscultation).
- Evaluation of chest X-ray or CT scans².
- Laboratory test³: haematology, biochemistry, urinalysis.
- Oxygen saturation (SpO₂).
- Evaluation of the eligibility.

Treatment period

Day 1 - enrolment, initiation of the treatment

Full list of the procedures is provided in Appendix 1.

- Evaluation of measures of clinical support.
- Assessment of the clinical status according to the 7-point ordinal scale.
- Assessment of the clinical status according to the NEWS scale and SOFA scale.
- Oropharyngeal/nasal (OP/N) sample.
- Haematology (only if this test was not performed at the screening).
- Blood chemistry (only if this test was not performed at the screening).
- Urinalysis (only if this test was not performed at the screening).
- Administration of the investigational product
- Physical examination (including lung auscultation).
- Collection of the efficacy data (oxygenation, mechanical ventilation, prolongation of

¹ Data obtained not later than 48 hours before signing the informed consent may be used.

² Recent chest X-ray/CT scans can be used, if the scans were obtained after the coronavirus disease (COVID-19) was diagnosed.

³ If the patient has results of laboratory tests that were performed within 48 before the enrolment, these results can be used to assess the clinical status and eligibility. These data can be used only if they are complete and include all parameters specified in the Protocol. Repeated laboratory tests on Visit 0 are not required in this case.

hospitalization).

- Recording of AEs.

Days 2...18

Full list of the procedures is provided in Appendix 1.

The visits are performed in the in-patient settings. If the patient is discharged before Day 17, the procedures will be performed at the outpatient visits to the clinic.

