6.3.8. Collection of efficacy data

The efficacy data (the need for oxygenation, the need for mechanical ventilation, continued hospitalization) will be collected daily during the study to assess the effectiveness of therapy during hospitalization. The selected scales are recommended for efficacy assessment by WHO².

The patient status will also be assessed using the following questionnaires/scales in accordance with the description of the study periods and the schedule of the study procedures.

Examples of the scales used in the study

¹ Temporary guidelines. Prevention, diagnosis, and treatment of the novel coronavirus infection (2019-nCoV). Version 2 (02/03/2020). Electronic source with free access: <https://static-i.rosminzdrav.ru/system/attachments/attaches/000/049/329/original/%D0%92%D1%80%D0%B5%D0%BC%D0%B5%D0%BD%D0%BD%D1%8B%D0%B5%D0%9C%D0%A0%2019-nCov%2003.02.2020%28%D0%B2%D0%B5%D1%80%D1%81%D0%B8%D1%8F%2029%20final.pdf?1580748451>. Access date: March 16, 2020.

² MASTER PROTOCOL. A Multi-centre, Adaptive, Randomized, Double-Blind, Placebo-Controlled Clinical Trial of the Safety and Efficacy of Investigational Therapeutics for the Treatment of COVID-19 in Hospitalized Patients. Electronic source with free access: <https://www.who.int/blueprint/priority-diseases/key-action/multicenter-adaptive-RCT-of-investigational-therapeutics-for-COVID-19.pdf>. Access date: March 13, 2020

Measures of clinical support

The following measures of clinical support will be evaluated on each day of hospitalization up to day 17:

- Hospitalization
- Oxygen requirement
- Non-invasive mechanical ventilation (via mask)
- Mechanical ventilator requirement (via endotracheal tube or tracheostomy tube)
- ECMO requirement

7-point ordinal scale

Recommended by WHO as the primary endpoint for evaluating the efficacy of coronavirus infection therapy¹.

The 7-point ordinal scale is an assessment of the clinical status at the first assessment of a given study day. Each day, the worse score for the previous day will be recorded. For example, on day 3, day 2 score is obtained and recorded as day 2. The scale is as follows:

1. Not hospitalized, no limitations on activities.
2. Not hospitalized, limitation on activities.
3. Hospitalized, not requiring supplemental oxygen.
4. Hospitalized, requiring supplemental oxygen.
5. Hospitalized, on non-invasive ventilation or high flow oxygen devices.
6. Hospitalized, on invasive mechanical ventilation or ECMO.
7. Death.

NEWS Score

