This score is based on 7 clinical parameters. The NEWS scale is used to evaluate efficacy and is recommended by WHO².

Literature shows that the NEWS score allows discriminating patients at risk of adverse outcomes [Smith et al., 2016].

This should be evaluated at the first assessment of a given study day. These parameters can be obtained from the hospital chart using the last measurement prior to the time of assessment. This is recorded for the day obtained. For example, on Day 3, Day 3 score is obtained and recorded as Day 3.

Physiological parameters	3	2	1	0	1	2	3
Respiration rate	≤8		9–11	12-20		21 -24	≥25
Oxygen saturation	≤91	92-93	94-95	≥96			

¹ WHO R&D Blueprint novel Coronavirus COVID-19 Therapeutic Trial Synopsis. Electronic source with free access: https://www.who.int/blueprint/priority-diseases/key-action/COVID-19_Treatment_Trial_Design_Master_Protocol_synopsis_Final_18022020.pdf. Access date: March 20, 2020.

² MASTER PROTOCOL. A Multi-centre, Adaptive, Randomized, Double-Blind, Placebo-Controlled Clinical Trial of the Safety and Efficacy of Investigational Therapeutics for the Treatment of COVID-19 in Hospitalized Patients. Electronic source with free access: <https://www.who.int/blueprint/priority-diseases/key-action/multicenter-adaptive-RCT-of-investigational-therapeutics-for-COVID-19.pdf>. Access date: March 13, 2020

Physiological parameters	3	2	1	0	1	2	3
Any Supplemental Oxygen		Yes		No			
Temperature	≤35.0		35.1-36.0	36.1-38.0	38.1-39.0	≥39.1	
Systolic BP	≤90	91-100	101-110	111-219			≥220
Heart Rate	≤40		41-50	51-90	91-110	111-130	≥131
Level of Consciousness				A			V, P, or U

Level of consciousness = alert (A), and arousable only to voice (V) or pain (P), and unresponsive (U).

SOFA Score

The SOFA scale is used to evaluate the clinical state and is recommended by WHO. Moreover, the SOFA scale was chosen because it is widely known, simple and applicable to most hospital settings. It was developed by the Sepsis Task Force of the European Society of Critical Medicine.

SOFA Organ Deficiency Assessment (Sepsis-related Organ Failure) is a point scale for assessing multiple organ failure in patients with septic syndrome who are in intensive care. This scale was created to quickly calculate and describe a number of complications in critically ill patients. The scale is intended rather for quick scoring and description of a number of complications than for predicting the outcome.

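### The primary endpoint compares Day 15 with a baseline that the plan never defines, and its own timing rules point to different assessments, some of them after dosing

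*Combined protocol and SAP*

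**What the plan says.** The Synopsis and sections 4.1, 7.1 and 9.1 give the primary endpoint as WHO 7-point status on Day 15 relative to baseline. Section 4.2 sets a single study group. Average change in WHO status and changes in NEWS and SOFA from baseline are secondary endpoints.

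On who enters and when treatment starts:
- Section 5.1, criterion 1: "The patient is already receiving, or the patient have been prescribed therapy with" Polyoxidonium. The Synopsis has the same content: "The patient is taking or have been prescribed" the drug. Neither limits earlier doses.
- Section 6.2: "Day 1 - enrolment, initiation of the treatment". Table 1 numbers all ten doses from study Day 1.

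On when the first WHO score is taken:
- Section 6.2 lists it among the Day 1 procedures ("Assessment of the clinical status according to the 7-point ordinal scale"), with no order relative to the dose.
- Table 1 enters admission, not a tick, in the Day 1 column for the WHO scale. NEWS and SOFA carry an ordinary tick there.
- Section 6.3.8 says "The 7-point ordinal scale is an assessment of the clinical status at the first assessment of a given study day" and then "Each day, the worse score for the previous day will be recorded", with the example that the Day 2 score is obtained on Day 3.
- For NEWS, section 6.3.8 has a different rule: "This is recorded for the day obtained".

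**The concern.** With no control group, within-patient change carries the primary efficacy inference wherever the endpoint is stated as a comparison with baseline. That change needs one starting point. If some patients start from a pre-dose score and others from a score taken on treatment, or if the time from baseline to Day 15 varies, the pooled change does not estimate one defined quantity.

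The gap also leaves a choice open. Sections 9.3 and 9.7 let methods be replaced or added once data are in hand, and the study is open. The choice between an admission score, a first Day 1 score and a worst Day 1 score could then be made after outcomes have been seen.

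**Working it through.** The plan gives no figure to reproduce here. The check sets the sections side by side and adds short illustrations.

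**Step 1. Is a baseline defined anywhere?** The only definition is in section 8.3.1: conditions present at screening count as baseline for adverse event reporting. It does not concern efficacy. Section 9.7.2.1 splits analyses by baseline severity without dating it, while section 5.1 classes severity at hospitalization. None of the nine procedures that section 6.2 lists before Day 1 is a WHO, NEWS or SOFA score.

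**Step 2. What can the baseline WHO score be under the text?**

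| Candidate | Source | Patient starting the drug on Day 1 | Patient already on the drug at enrolment |
|---|---|---|---|
| Status at admission | Table 1 | Pre-dose | Pre-dose only if the drug was started after admission |
| First assessment on Day 1 | Section 6.2; first rule in 6.3.8 | Pre-dose only if scored before the dose, which is not required | Post-dose |
| Worst status over Day 1, obtained on Day 2 | Second rule in 6.3.8 | Can include hours after the dose | Post-dose |

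**Step 3. Are admission and Day 1 the same moment?** Nothing requires it. The Table 1 note for chest imaging and ECG treats admission as before enrolment.

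**Step 4. Interval from baseline to Day 15.** Table 1 allows Day 15±1. With a gap of L days from admission to enrolment, the interval is (15 − 1) ± 1 + L.
- Day 1 baseline, or L = 0: 13 to 15 days.
- L = 3: 16 to 18 days.
- L = 7: 20 to 22 days.

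The gaps of 3 and 7 days are assumptions. Section 9.7.2.1 also lets the primary day move, so these intervals hold only while Day 15 is kept.

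**Step 5. Post-dose scores, assuming a Day 1 baseline.** The Synopsis plans at least 50 patients; 50 is used here. The share already treated is not in the documents, so 10, 30 and 50% are assumed.
- First-assessment rule, new starters scored before dosing: 50 × 0.10 = 5, 50 × 0.30 = 15, 50 × 0.50 = 25 post-dose baselines.
- Worst-of-day rule: the scored day contains the Day 1 dose, so up to 50 of 50 scores can include post-dose time.

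**Step 6. Mixing the two scoring rules.** Higher is worse, so the worst score of a day is at least as high as the first score of that day. A single score at baseline set against a daily worst on Day 15 can only make improvement look equal or smaller than with single scores at both; the reverse mix can only make it look equal or larger.

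**Step 7. Precision of an analysis without already-treated patients.** As a simple guide, for a proportion of 50% the 95% half-width is 1.96 × √(0.25/n): 13.9 points at n = 50, 14.6 at 45, 16.6 at 35 and 19.6 at 25.

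**The case against.** The strongest reply is that admission is the intended WHO baseline. Table 1 says so in the Day 1 cell, time to improvement runs from admission (section 4.1), and severity is classed at hospitalization (section 5.1). Table 1 also keeps that cell apart from its daily column, so the previous-day rule may govern only the daily scores. This stands in part: under that reading, the counts in step 5 do not follow for anyone who started the drug after admission. It does not settle the matter, because section 6.2 still lists a Day 1 score, no text names either one as baseline, and criterion 1 does not say that treatment began after admission.

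A second reply is that the two sentences in 6.3.8 agree: at the first assessment each day, record the worst of the day before. If that rule covers Day 1, the Day 1 score can include post-dose hours even in new starters.

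Third, existing records may already identify these patients. Sections 6.2 and 6.3.2 collect previous treatment, and section 13.2 requires source records of previous and concomitant treatment and of the prescribed study treatment. First-dose date should therefore largely be recoverable; what is missing is an explicit field for it and for the number of prior doses.

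A reader might infer that change from baseline is the only efficacy contrast. It is not: sections 4.2 and 9.7.2.1 state the primary endpoint as Day 15 status alone, and mortality, hospital stay and time to discharge are not changes from baseline.

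**Conclusion.** The concern holds as an undefined baseline with conflicting timing rules. Two conflicts need reconciling: the time of the first WHO score (sections 6.2 and 6.3.8, Table 1), and criterion 1 against the Day 1 label and dosing calendar. The first conflict affects new starters as well, so the point does not depend on how many patients were already treated.

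Its size cannot be fixed from the documents. The counts of 5, 15 and 25 of 50, and up to 50 of 50, are illustrations that assume a Day 1 baseline; the longer intervals assume an admission baseline and a gap. The share already treated may be small.

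A reader might go further and infer that the primary result is biased in the drug's favour, or that a known part of the sample has a post-dose baseline. The documents support neither. They give no share, and the bias could run either way: a worst-of-day or admission baseline can count early recovery or change before enrolment as improvement, while an on-treatment baseline omits change since the first dose.

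**What to change.** 1. In section 9, define the efficacy baseline as the last WHO score, and NEWS and SOFA where available, before the first Polyoxidonium dose, taken from hospital records if needed. The plan already allows this kind of source for NEWS: "These parameters can be obtained from the hospital chart using the last measurement prior to the time of assessment". Align sections 6.2 and 6.3.8 and Table 1 with the definition.
2. In section 6.3.8, keep one WHO scoring rule and apply it alike at baseline and on Day 15, with a single assessment at both.
3. In section 9.7.2.1, give the date of the baseline severity, consistent with section 5.1.
4. Add eCRF fields for first-dose date and number of doses before enrolment, filled from the treatment records already required.
5. Keep eligibility, the visit calendar and ITT as the main analysis. Pre-specify an added analysis of patients enrolled on or before the day of first dose, and report already-treated patients separately with their interval from baseline to Day 15.

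The sponsor must reconcile criterion 1 with the Day 1 label and the dosing calendar; no clinical rule is proposed here.

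The cost is one definition, wording changes, two eCRF fields and one further analysis. There are three drawbacks. The added analysis is smaller (step 7). Pre-dose NEWS or SOFA may be missing for already-treated patients, and section 9.4 bars substitution. In the main analysis these patients keep a longer interval from baseline to Day 15, and they must have survived to enrolment, which is why they are also reported separately.

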5.2. Exclusion criteria

1. Pregnancy and lactation.
2. Pathological conditions that make participation in the study impossible for the patient (as judged by the investigator).
3. Participation in any other clinical study during this study, including participation in a clinical study within 30 days before the informed consent.
4. Increased sensitivity to any component of the investigational product.
5. Acute or chronic renal failure.

5.3 Withdrawal criteria

1. The investigator decided that withdrawal from the study is in the patient's interests.
2. Withdrawal of the informed consent (the patient does not want to continue participation in the study).
3. Serious deviation from the study protocol.
4. Idiosyncrasy to the investigational products that developed during the treatment period.
5. AE/SAE that requires an examination and/or treatment that would affect the study procedures significantly.
6. Patient non-compliance.
7. The patient was enrolled by mistake.
8. The patient receives/needs an additional treatment that could affects result of the study or the patient safety.
9. Other conditions or events that require patient withdrawal, as judged by the study

doctor.

The subjects that were withdrawn from the study because of an AE/SAE will be followed until the AE/SAE is resolved or the patient is stabilized.

A subject will be considered lost to follow-up if he or she fails to appear for a follow-up assessment and cannot be contacted with good effort. These efforts will be documented in the subject's record.

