Open multi-centre observational study of efficacy and safety of a medicinal

	
product.
 
The clinical efficacy will be assessed by changes in the patient's clinical status, duration of hospitalization, oxygenation/mechanical ventilation. The clinical examination will include clinical, laboratory, and instrumental investigations according to the current guidelines on treatment of COVID-19 in the Russian Federation.

POPULATION	Hospitalized patients of 18 years and older with confirmed COVID-19.
SAMPLE SIZE	At least 50 patients
TREATMENT ALLOCATION	All study subjects will receive treatment with Polyoxidonium, lyophilizate, 12 mg, in addition to the standard treatment
DIAGNOSIS	Verified COVID-19

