5.4. Patient withdrawal

If the patient was not administered at least one dose of the investigational product and left the study for any reason, then further monitoring is not carried out, and data of this patients are not included in the statistical analysis.

Unless the patient withdraws consent, those who discontinue study drug early should remain in the study, if possible, for further acquisition of endpoint measurements. The reason for patient discontinuation of study drug should be documented in the case report form.

The investigator submits the data on the patients excluded from the study to the Sponsor and the monitor of the study within 24 hours in the form of a report that includes the patient's status at the end of the study.

Patient status at the end of the study:

1. *Completed the study.*
2. *Did not complete the study because of:*
 - The investigator's mistake.
 - Adverse events.
 - Serious adverse events.
 - Pregnancy.
 - Protocol violations.
 - The patient's wish to leave the study.
 - The patient did not show up for a visit.
 - Other reasons (specify).

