6.4. Concomitant therapy

Standard therapy for coronavirus infection (COVID-19, SARS-CoV-2) will be used in accordance with international and national guidelines that will be in force at the time of the study. The patient's status should be monitored during medical care to identify signs of clinical deterioration, such as rapidly progressive respiratory failure and sepsis, and to prescribe relevant treatment. Patients infected with 2019-nCoV should receive supportive symptomatic therapy¹. The comorbid conditions and complications should be treated in accordance with clinical guidelines, standards of medical care for these diseases, conditions, and complications in force in the relevant country at the time of the planned study.

If the concomitant condition is not an inclusion/exclusion criterion, the treatment of such condition within this protocol should follow the standard of care.

¹ Temporary guidelines. Prevention, diagnosis, and treatment of the novel coronavirus infection (2019-nCoV). Version 2 (02/03/2020). Electronic source Access: https://static-1.rosminzdrav.ru/system/attachments/attaches/000/049/329/original/%D0%92%D1%80%D0%B5%D0%BC%D0%B5%D0%BD%D0%BD%D1%8B%D0%B5_%D0%9C%D0%A0_2019-nCov_03.02.2020_%28%D0%B2%D0%B5%D1%80%D1%81%D0%B8%D1%8F_2%29_final.pdf?1580748451, free. Access date: March 16, 2020.

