8.3. Recording and reporting of adverse events

8.3.1. Definition of Adverse Event (AE)

Adverse event means any untoward medical occurrence associated with the use of an intervention in humans, whether considered intervention related or not. An AE can therefore be any unfavourable and unintended sign (including an abnormal laboratory finding), symptom, or disease temporally associated with the use of medicinal (investigational) product.

Any medical condition that is present at the time that the subject is screened will be considered as baseline and not reported as an AE. However, if the severity of any pre-existing medical condition increases, it should be recorded as an AE.

Given the nature of severity of the underlying illness, subjects will have many symptoms and abnormalities in vitals and laboratory. All Grade 3 and 4 AEs will be captured as AEs in this study.

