9.4. Drop-outs, withdrawn patients, and missing data

No missing data will be substituted. The missing/omitted data will not be considered during statistical analysis.

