13.4. Data collection

Data that are collected during the study are recorded in the eCRF.

eCRFs must be filled in within the time period agreed with the Sponsor. If a patient is withdrawn from the study, the eCRF is filled in up to the withdrawal and includes the reason for withdrawal.

The study doctor is responsible for ensuring completeness and accuracy of the data in the eCRF. Data in the eCRF should be confirmed by the source records.

The duties of the Monitor include verifying compliance of the eCRF with the source records. The study doctor shall provide the source records to the Monitor for verification.

The Monitor shall inform the study doctor about any discrepancies in the data. The monitor does not have the right to make corrections to the eCRF.

Corrections to the eCRF are made by the investigator or a member of the study team who has the right to enter data in the CRF in accordance with the relevant instructions.

AEs and concomitant medications will be coded according to the most current versions of MedDRA and WhoDrug or ATC, respectively.

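### Withdrawal criteria 5 and 8 can remove worsening patients from the Day 15, Day 29 and 28-day mortality results, which would bias a single-group result favourably

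*Combined protocol and SAP*

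**What the plan says.** All references are to the combined protocol and SAP. The study has one treated group; the Synopsis gives its size as "At least 50 patients", with no calculation behind it. The primary outcome is the WHO 7-point status on Day 15 against baseline (4.1). Day 29 status and 28-day mortality are among the secondary outcomes.

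Two withdrawal criteria in 5.3 matter here. Criterion 5 is "AE/SAE that requires an examination and/or treatment that would affect the study procedures significantly". Criterion 8 is "The patient receives/needs an additional treatment that could affects result of the study or the patient safety". Section 8.3.1 adds that "if the severity of any pre-existing medical condition increases, it should be recorded as an AE", and 6.4 has sites monitor patients "to identify signs of clinical deterioration, such as rapidly progressive respiratory failure and sepsis, and to prescribe relevant treatment".

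The consequences are spread over several sections:

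- 4.5: withdrawal is from the study. It is worded as something the investigator may do, and sites are asked to try hard to keep patients in for their planned assessments.
- 5.4: "those who discontinue study drug early should remain in the study, if possible, for further acquisition of endpoint measurements", unless consent is withdrawn.
- 6.1: a withdrawn patient has an Early Termination Visit with the Day 29 procedures.
- 13.4: "If a patient is withdrawn from the study, the eCRF is filled in up to the withdrawal".
- 9.4: "No missing data will be substituted", and missing values play no part in the analysis.
- 5.5: withdrawn patients are not replaced.
- 11.8: a patient who met a withdrawal criterion but stayed in is an example of a significant deviation, and patients with significant deviations are to be left out of the final efficacy analysis.
- 9.7.2: ITT, defined in 9.6 as all enrolled patients, is the main efficacy population.

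**The concern.** The upper end of the primary scale is escalating respiratory support and death, so the unfavourable outcome is worsening. Worsening also makes criteria 5 and 8 more likely to be met. Loss of the Day 15 value can therefore depend on what that value would have been, and ignoring such values moves the result towards improvement.

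No control group undergoes the same selection, so nothing offsets it. Keeping every enrolled patient in the ITT set does not help by itself: under 9.4 a patient without a Day 15 value contributes nothing. Section 4.3 acknowledges that withdrawal may introduce systematic error, but its remedy is to gather the latest available data and the reason for stopping, which is not an outcome on Day 15 or Day 29.

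**Working it through.** **Step 1: follow one patient who meets criterion 5 or 8 before Day 15.**

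- If withdrawn from the study, the eCRF closes (13.4), no Day 15 or Day 29 score is required, and the gap is ignored (9.4).
- If kept, the patient falls under the 11.8 example and is removed from the efficacy analysis, contrary to 9.7.2.
- If only the drug is stopped, 5.4 keeps the patient in for endpoints where possible. But 5.4 does not say that it governs patients who meet a 5.3 criterion, and its own status list gives adverse events and serious adverse events as reasons for not completing the study.

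On the first two routes the patient can drop out of the Day 15 result. The third points the other way, and no section says which prevails.

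**Step 2: see what the protective provisions deliver.** The Early Termination Visit records WHO, NEWS and SOFA scores at withdrawal; no rule says how they enter the Day 15 or Day 29 analysis. Follow-up under 5.3 and 5.6 covers only AE/SAE withdrawals, ends at resolution or stabilisation, and names no WHO score. A criterion 8 withdrawal without an adverse event has no further follow-up.

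**Step 3: size.** The plan states no figure to reproduce. The only input from the documents is N = 50 (Synopsis, a minimum). The number improved x, the number of non-improvers lost w, and the absence of lost improvers are assumptions.

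True share = x/N; reported share = x/(N − w); difference = xw/[N(N − w)]. With x = 33, so 17 non-improvers:

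- w = 0: 33/50 = 66%, no bias.
- w = 5: 33/45 = 73.3%; difference 165/2250 = 7.3 points.
- w = 10: 33/40 = 82.5%; difference 330/2000 = 16.5 points.

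A second assumed case takes 10 of 50 deteriorating and reports the share not worse, with exact 95% intervals:

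- none lost: 40/50 = 80.0% (66.3 to 90.0)
- 5 lost: 40/45 = 88.9% (75.9 to 96.3)
- all 10 lost: 40/40 = 100% (91.2 to 100)

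In the same case, assuming a change of −2 points for the other 40 and +1 for the 10 who deteriorate, the mean change is (−80 + 10)/50 = −1.40 with nobody lost and (−80 + 5)/45 = −1.67 with 5 lost.

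For 28-day mortality, assume 5 deaths in 50 (10.0%). If 2 of those patients are withdrawn before death and not counted, the reported figure is 3/48 = 6.25%.

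**The case against.** A reader might infer that every patient who deteriorates loses the Day 15 and Day 29 outcomes, that those data are never collected, and that mortality is driven towards zero. The documents do not support that:

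- Guideline COVID-19 therapy is planned background treatment (6.4), so prescribing for deterioration does not by itself meet criterion 8. Oxygen, ventilation and ECMO are levels of the primary scale.
- Criterion 5 requires a significant effect on study procedures, and those procedures are routine care (6.2).
- Section 4.5 makes withdrawal discretionary and urges retention. Section 5.4, which directly follows the criteria, can be read as meant for these patients.
- The Early Termination Visit would record a worsened status.
- Death is a serious adverse event, and such events are followed and reported, even when learned of after study completion (8.3.2, 8.3.6). Some deaths after withdrawal would surface.
- The share withdrawn is assumed throughout, and zero is possible.

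All of this stands against certainty. It does not remove the problem. Section 11.8 penalises a site that uses the discretion in 4.5 to keep a patient. No section defines which additional treatment meets criterion 8, so selection can differ by site. A status at withdrawal is not a status on Day 15, and event reporting is not systematic vital status to Day 29.

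**Conclusion.** The point holds as a risk built into the plan, not as a certain loss. Criteria 5 and 8, taken with 9.4, 11.8 and 13.4, allow worsening patients to be absent from the Day 15, Day 29 and 28-day mortality results, while 4.5, 5.4 and 9.7.2 pull the other way without settling the matter. Where such loss occurs, the bias favours the drug.

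The size runs from zero to large according to how sites apply the criteria. The illustrated gains of 7.3 and 16.5 percentage points assume 50 patients, 33 improvers, and loss of non-improvers only. The direction depends on loss being more frequent among patients who do badly; if improvers were lost in the same proportion, the reported share would not shift. The matter should be settled before data collection, because an outcome that was not recorded cannot be recovered at analysis.

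**What to change.** Separate stopping the drug from ending outcome collection:

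- **5.3, 4.5 and 5.4:** reconcile them so that only withdrawal of consent ends outcome collection. For every enrolled patient who received at least one dose, record the WHO scale on Day 15 and Day 29 and vital status to Day 29, by chart or by phone (6.2 already allows remote contact after discharge), and keep the patient in the ITT analysis.
- **13.4:** continue the eCRF for these items after a patient meets a withdrawal criterion.
- **11.8:** remove the example about a patient who met a criterion but was not excluded, and remove the exclusion of significant deviations from the main (ITT) efficacy analysis. Any such exclusion belongs in a sensitivity analysis.
- **Section 9:** state that an Early Termination score does not replace the Day 15 or Day 29 score. Add a worst-case sensitivity analysis in which patients still missing count as not improved and unknown vital status counts as death. In the first illustration this returns 33/50 = 66% whether 5 or 10 patients are lost.

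The cost is protocol wording and a few chart checks or calls. It needs no extra patients and no invasive procedures. NEWS and SOFA cannot be fully obtained by phone and would stay missing for some patients. Whether treatment continues is a clinical matter and is not part of this change.
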